### **10.3 EXPLORATORY EFFICACY VARIABLE - ELASTICITY**

Elasticity is collected at baseline and Days 90 and 180. Descriptive statistics (sample size, mean, median, standard deviation, minimum, maximum) of elasticity and of the change from baseline will be presented at each visit. The two-sided 95% confidence interval of the means will be presented.

## 11 SAFETY ANALYSIS

All adverse events (AEs) will be coded using the standardized Medical Dictionary for Regulatory Activities (MedDRA) central coding dictionary, version 19.1 or greater. All analyses described below will be performed on the Safety Population.

### 11.1 NUMERICAL RATING SCALE (NRS)

NRS will be summarized for the Safety Population at Days 30, 60 (on the sample of size 30), 90, and 180. Change from Day 30 to Days 60, 90 and 180, and change from Day 90 to Day 180 will also be summarized. The summary consists of the sample size, mean, median, standard deviation, minimum and maximum.

### 11.2 ALL ADVERSE EVENTS

Summaries of incidence rates and relationship to the investigational device of individual treatment emergent AEs (TEAE) by System Organ Class (SOC) and Preferred Term (PT) will be prepared. A treatment emergent adverse event is defined as an event that started or worsened in severity at or after the first attempt at treatment. Because a subject may experience more than one TEAE, summaries will provide both the number of subjects and the number of events within a reporting period. Percentages provided will be the percent of subjects in the Safety Population experiencing one or more adverse events.

A listing of all adverse events will include the subject number, AE number, days since procedure, the AE SOC and PT, the severity of AE, whether or not the AE is classified as serious (SAE), the relationship of the AE to the investigational device or procedure, the action taken, the outcome, and the adjudication status.

AEs will be recorded for all enrolled subjects to time of withdrawal, and reported in a table for all Safety subjects.

### 11.3 ADVERSE EVENTS LEADING TO WITHDRAWAL

A summary of incidence rates (frequencies and percentages) of TEAEs leading to study withdrawal, by SOC and PT will be prepared for the Safety Population. A data listing of AEs leading to withdrawal will also be provided, displaying details of the event(s) captured on the CRF.

### 11.4 SERIOUS ADVERSE EVENTS (SAE)

Summaries of incidence rates and relationship to the investigational device/procedure of individual serious TEAEs SAEs by SOC and PT will be prepared. Summaries will provide both the number of subjects and the number of events within a reporting period. Percentages provided will be the percent of subjects experiencing one or more serious adverse events. A data listing of SAEs will also be provided, displaying details of the event(s) captured on the CRF.

### 11.5 DEVICE OR PROCEDURE RELATED ADVERSE EVENTS

Summaries of incidence rates of device and procedure related AEs and SAEs by SOC and PT will be prepared. Summaries will provide both the number of subjects and the number of events within a reporting period. Percentages provided will be the percent of subjects experiencing one or more device or

procedure related adverse events. Data listings of device and procedure related AEs and SAEs will also be provided, displaying details of the event(s) captured on the CRF.

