10.5. Severity Assessment

If required on the adverse event case report forms, the investigator will use the adjectives MILD, MODERATE, or SEVERE to describe the maximum intensity of the adverse event. For purposes of consistency, these intensity grades are defined as follows:

MILD	Does not interfere with subject's usual function.
MODERATE	Interferes to some extent with subject's usual function.
SEVERE	Interferes significantly with subject's usual function.

Investigational Device: ThermiRF

Protocol No.: Thermi_0005

Version Date: Final 10-May-2016

Note the distinction between the severity and the seriousness of an adverse event. A severe event is not necessarily a serious event. For example, a headache may be severe (interferes significantly with subject's usual function) but would not be classified as serious unless it met one of the criteria for serious adverse events, listed above.

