10.6. Causality Assessment

The investigator's assessment of causality must be provided for all adverse events (serious and non-serious). An investigator's causality assessment is the determination of whether there exists a reasonable possibility that the ID caused or contributed to an adverse event. If the investigator's final determination of causality is unknown and the investigator does not know whether or not ID caused the event, then the event will be handled as "related to ID" for reporting purposes. If the investigator's causality assessment is "unknown but not related to ID", this should be clearly documented on study records.

In addition, if the investigator determines a serious adverse event is associated with study procedures, the investigator must record this suspected causal relationship in the source documents and CRF, as appropriate, and report such an assessment in accordance with the serious adverse event reporting requirements, if applicable.

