11.5.4 Safety Analysis

All safety analyses and summaries will be based on the Safety population. The number and percentage of subjects reporting AEs during the study will be tabulated by MedDRA system organ class (SOC) and preferred term within each SOC. SOCs will be listed in order of descending frequency. Preferred terms will be listed in order of descending frequency within each SOC. Summaries and listings will be provided for subjects reporting SAEs, subjects experiencing AEs related to study medication and subjects withdrawing due to an AE.

Subjects experiencing serious adverse events, treatment-related adverse events and discontinuation from the study due to adverse events will also be summarized.

Treatment-related adverse events will include events marked as being at least possibly or probably related to the study treatment. Adverse events will be presented by severity and by relation to treatment.

Subject disposition at Visit 1 will be presented. Enrollment status with respect to number of subjects enrolled, completed, lost-to-follow and discontinuation regardless of reason will be presented.

Concomitant medications will be summarized.

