**NOTE: This SOC and PT structure to be carried forward to tables**

Listing 11 Summary of Adverse Events by SOC and PT						
Subject ID	Adverse Event Number	SOC (Preferred Term)	Days Post Procedure	Any Adverse Event	Any Serious Adverse Event	Event Related to Study Treatment
XX-XXX	XX	XX	XX	XX	XX	XX

**Sponsor:** ThermiGen, LLC.  
**Protocol Number:** Thermi\_0005  
**Protocol:** *An Open-Label, Single-Center, Single-Treatment, Safety and Effectiveness Evaluation of Percutaneous Radiofrequency in Achieving Submental Lift*  
**Version:** Protocol Rev. A; SAP Rev. B

Table 12									
Overall Treatment Emergent Serious Adverse Events Summary by System Organ Class and Preferred Term [1] [2]									
Safety Population									
		After Treatment Prior to Day 30		After Day 30, up to Day 60		After Day 60, up to Day 90		After Day 90, up to day 180	
		N=XX	N=XX	N=XX	N=XX	N=XX	N=XX	Total	
		# Events	Subjects w/Event % (n/N)	# Events	Subjects w/Event % (n/N)	# Events	Subjects w/Event % (n/N)	# Events	Subjects w/Event % (n/N)
All Serious Adverse Events		XX	XX.X (X/XX)	XX	XX.X (X/XX)	XX	XX.X (X/XX)	XX	XX.X (X/XX)
each System Organ Class		XX	XX.X (X/XX)	XX	XX.X (X/XX)	XX	XX.X (X/XX)	XX	XX.X (X/XX)
each Preferred Term		XX	XX.X (X/XX)	XX	XX.X (X/XX)	XX	XX.X (X/XX)	XX	XX.X (X/XX)

[1] Events reported as adjudicated or by site if not adjudicated

[2] Denominators of time points are subjects past the visit window or with an event

Listing 12						
Summary of Serious Adverse Events by SOC and PT						
Subject ID	Adverse Event Number	SOC (Preferred Term)	Days Post Procedure	Any Adverse Event	Any Serious Adverse Event	Event Related to Study Treatment
XX-XXX	XX	XX	XX	XX	XX	XX

**Sponsor:** ThermiGen, LLC.  
**Protocol Number:** Thermi\_0005  
**Protocol:** *An Open-Label, Single-Center, Single-Treatment, Safety and Effectiveness Evaluation of Percutaneous Radiofrequency in Achieving Submental Lift*  
**Version:** Protocol Rev. A; SAP Rev. B

Table 13										
Device-Related Treatment Emergent Adverse Events Summary by System Organ Class and Preferred Term [1] [2]										
Safety Population										
	After Treatment Prior to Day 30		After Day 30, up to Day 60		After Day 60, up to Day 90		After Day 90, up to day 180		Total	
	N=XX		N=XX		N=XX		N=XX		N=XX	
	# Events	Subjects w/Event % (n/N)	# Events	Subjects w/Event % (n/N)	# Events	Subjects w/Event % (n/N)	# Events	Subjects w/Event % (n/N)	# Events	Subjects w/Event % (n/N)

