All Device-related AEs	XX	XX.X (X/XX)	XX	XX.X (X/XX)	XX	XX.X (X/XX)	XX	XX.X (X/XX)	XX	XX.X (X/XX)
each System Organ Class	XX	XX.X (X/XX)	XX	XX.X (X/XX)	XX	XX.X (X/XX)	XX	XX.X (X/XX)	XX	XX.X (X/XX)
each Preferred Term	XX	XX.X (X/XX)	XX	XX.X (X/XX)	XX	XX.X (X/XX)	XX	XX.X (X/XX)	XX	XX.X (X/XX)

[1] Events reported as adjudicated or by site if not adjudicated

[2] Denominators of time points are subjects past the visit window or with an event

Listing 13						
Summary of Adverse Events Related to Study Treatment						
Subject ID	Adverse Event Number	SOC (Preferred Term)	Days Post Procedure	Any Adverse Event	Any Serious Adverse Event	Event Related to Study Treatment
XX-XXX	XX	XX	XX	XX	XX	XX

**Sponsor:** ThermiGen, LLC.  
**Protocol Number:** Thermi\_0005  
**Protocol:** *An Open-Label, Single-Center, Single-Treatment, Safety and Effectiveness Evaluation of Percutaneous Radiofrequency in Achieving Submental Lift*  
**Version:** Protocol Rev. A; SAP Rev. B

Table 14 Device-Related Treatment Emergent Serious Adverse Events Summary by System Organ Class and Preferred Term [1] [2]										
Safety Population										
	After Treatment Prior to Day 30		After Day 30, up to Day 60		After Day 60, up to Day 90		After Day 90, up to day 180		Total	
	N=XX	N=XX	N=XX	N=XX	N=XX	N=XX	N=XX	N=XX		
	# Events	Subjects w/Event % (n/N)	# Events	Subjects w/Event % (n/N)	# Events	Subjects w/Event % (n/N)	# Events	Subjects w/Event % (n/N)	# Events	Subjects w/Event % (n/N)
All Device-related, Serious AEs	XX	XX.X (X/XX)	XX	XX.X (X/XX)	XX	XX.X (X/XX)	XX	XX.X (X/XX)	XX	XX.X (X/XX)
each System Organ Class	XX	XX.X (X/XX)	XX	XX.X (X/XX)	XX	XX.X (X/XX)	XX	XX.X (X/XX)	XX	XX.X (X/XX)
each Preferred Term	XX	XX.X (X/XX)	XX	XX.X (X/XX)	XX	XX.X (X/XX)	XX	XX.X (X/XX)	XX	XX.X (X/XX)

[1] Events reported as adjudicated or by site if not adjudicated

[2] Denominators of time points are subjects past the visit window or with an event

Listing 14 Summary of Serious Adverse Events Related to Study Treatment						
Subject ID	Adverse Event Number	SOC (Preferred Term)	Days Post Procedure	Any Adverse Event	Any Serious Adverse Event	Event Related to Study Treatment
XX-XXX	XX	XX	XX	XX	XX	XX

**Sponsor:** ThermiGen, LLC.  
**Protocol Number:** Thermi\_0005  
**Protocol:** *An Open-Label, Single-Center, Single-Treatment, Safety and Effectiveness Evaluation of Percutaneous Radiofrequency in Achieving Submental Lift*  
**Version:** Protocol Rev. A; SAP Rev. B

Table 15									

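### The related-event breakdowns in the SAP shells cover the device only, although SAP 11.5 also requires procedure-related events, and no summary by severity is planned although Protocol 11.5.4 requires one

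*SAP*

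**What the plan says.** SAP 11.5: "Summaries of incidence rates of device and procedure related AEs and SAEs by SOC and PT will be prepared". The same section bases the percentages on subjects with one or more events related to the device or to the procedure. SAP 11.4 asks for the relationship of serious events to device/procedure.

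SAP 13 names Attachment 2 as the planned output for the study report. There, Table 10 has one *Device Related* row under all adverse events and one under serious adverse events. Table 13 is titled "Device-Related Treatment Emergent Adverse Events Summary by System Organ Class and Preferred Term" and Table 14 "Device-Related Treatment Emergent Serious Adverse Events Summary by System Organ Class and Preferred Term". No shell has a procedure-related row or table.

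On severity, Protocol 11.5.4 says: "Adverse events will be presented by severity and by relation to treatment". SAP 11.2 lists the content of the adverse event listing, including "the severity of AE, whether or not the AE is classified as serious (SAE"). On collection, Protocol 10.5 says: "If required on the adverse event case report forms, the investigator will use the adjectives MILD, MODERATE, or SEVERE".

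**The concern.** The treatment is more than the device. Under Protocol 8.2 it includes up to three small incisions, tumescent infusion with lidocaine and epinephrine, and insertion of the probe. Protocol 9.3 lists infection, scarring and postoperative pain among the events to be collected. An investigator could reasonably attribute any of these to the procedure and not to the radiofrequency device. If the shells are followed, such an event appears in no summary of related events, and the reported rate is not the quantity that SAP 11.5 defines.

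The trial has no comparator arm, so the absolute rate of related events, and how severe they were, is central to the safety result. Without a summary by severity, mild and severe events under the same preferred term share one count.

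**Working it through.** The plan gives no figure on this point, so there is none to reproduce. The check sets the SAP and Protocol text against the six adverse event tables (10 to 15) and their six listings.

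| Requirement | Source | What the shells provide |
|---|---|---|
| Procedure-related AEs by SOC and PT | SAP 11.5 | None; Table 13 is device-related |
| Procedure-related SAEs by SOC and PT | SAP 11.5 | None; Table 14 is device-related |
| Subjects with an event related to either | SAP 11.5 | No cell for this number in any table |
| SAE relationship to device/procedure | SAP 11.4 | Table 12 has no split; Table 10 and Table 14 show device only |
| AEs by severity | Protocol 11.5.4 | No severity row or column in Tables 10 to 15 |
| Severity in the AE listing | SAP 11.2 | No such column in Listings 10 to 15 |
| Relationship to device or procedure in the AE listing | SAP 11.2 | One column, relation to study treatment |

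Counts: tables with a procedure-related breakdown, 0 of 6; tables with severity, 0 of 6; listings with a severity column, 0 of 6; tables confined to device-related events, 2 of 6 (Tables 13 and 14), plus two rows of Table 10.

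Path of one event judged related to the procedure but not to the device:

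1. It is counted in the all-events row of Table 10 and in Table 11. It is also counted in Table 12 if serious and in Table 15 if it led to withdrawal, because these tables ignore relationship.
2. It is not counted in the *Device Related* rows of Table 10, nor in Tables 13 or 14.
3. It is therefore missing from every related-event summary, although SAP 11.5 puts the subject in the numerator.

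Size. Let k be the number of treated subjects whose only related events are procedure-related. In the Total column of Table 13 the rate falls short of the SAP 11.5 rate by k/N. With N = 70, assuming every planned subject is treated, each such subject contributes 1/70 = 0.014, or about 1.4 percentage points. The documents give no basis for k. It is zero if every procedure-related event is also attributed to the device.

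Severity. Protocol 11.6 leaves table specifications to the SAP. SAP 11.2 to 11.5 describe summaries by SOC, PT and relationship, and none by severity. The gap is therefore in the SAP text as well as in the shells. The SAP also needs severity for its own definition of a treatment-emergent event, which includes events that worsened, while Protocol 10.5 makes grading conditional on the CRF.

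**The case against.** The strongest reply is that the device-only titles may be a labelling slip. Listings 13 and 14, which support Tables 13 and 14, are titled by relation to study treatment, and all six listings carry a study-treatment column. SAP 11.5 already words the percentage correctly. The CRF is not supplied, so one cannot see whether it has one causality field or two. Protocol 10.6 also sets a low threshold (a reasonable possibility that the device caused or contributed), so few events may be procedure-only. This stands as a limit on size. It does not settle what the tables will contain: table titles and listing titles disagree, and the programmer works from the shells.

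A reader might infer more than the documents support:

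- That the shells tabulate only device-related events. They do not: Tables 10, 11, 12 and 15 count treatment-emergent events whatever their relationship, so total harm is still shown.
- That the report could not show severity. SAP 11.2 requires it per event in the listing, and that section was written after review of the CRFs. The listing shells also omit action taken, outcome and adjudication status, so they look abbreviated generally. What is not planned is a summary.
- That a mild erythema and a severe burn would be indistinguishable. Tables 11 and 13 are by preferred term, so differently coded events sit on different rows. Grades merge within a term and in the SOC and total rows.
- That the Protocol contradicts itself on unknown causality. Section 10.6 addresses the case "If the investigator's final determination of causality is unknown and the investigator does not know whether or not ID caused the event" and handles it as related for reporting. Section 11.5.4 says "Treatment-related adverse events will include events marked as being at least possibly or probably related to the study treatment". That wording is inclusive and does not shut out unknown cases. At most the SAP is silent.

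**Conclusion.** Two gaps are established by comparing texts. First, the related-event summaries in the shells are limited to the device, against SAP 11.5 and 11.4. Second, the by-severity presentation required by Protocol 11.5.4 is planned nowhere in the SAP, and the listing shells omit a severity column that SAP 11.2 requires.

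The first gap affects only the related-event breakdown, and only events attributed to the procedure and not to the device. Its numerical size cannot be derived. The conclusion rests on the shells being followed as written and on the CRF allowing a separate attribution to the procedure. The second gap needs neither condition for the missing summary, because the SAP text itself plans none.

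**What to change.** - Table 10: add *Procedure related* and *Device or procedure related* rows under both all adverse events and serious adverse events.
- Tables 13 and 14: show device, procedure, and either.
- Add one table of treatment-emergent events by SOC, PT and maximum severity, overall and for related events, and name it in SAP 11.2.
- AE listings: add severity and separate columns for relationship to device and to procedure.
- Before programming, confirm that the CRF records severity (Protocol 10.5 is conditional) and procedure relationship for non-serious events (Protocol 10.6 states this explicitly only for serious ones).
- If procedure relationship is not collected separately, relabel the Table 10 rows and Tables 13 and 14 as treatment-related, in line with Listings 13 and 14 and Protocol 11.5.4, and align SAP 11.4 and 11.5.

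The cost is some shell editing and one extra table, with no new data if the CRF already holds both fields. The related-event rate may come out less favourable.

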### 11.6 DEATHS

Should any subjects die during the course of this study, relevant information will be supplied in a data listing.

## 12 PLANNED SUBGROUP ANALYSES

### 12.1 SEX

To understand any potential sex differences which may be relevant to this study, the primary and secondary efficacy endpoints will be evaluated for each sex separately with the results side by side and presented in a table for the ITT analysis set. The purpose of this analysis is to assess consistency across the subgroups of sex.

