6. INVESTIGATIONAL PLAN

6.1. Overall Study Design and Plan

This is an open-label, single-center, single-treatment prospective evaluation of the ThermiRF device in the treatment of submental skin laxity. The purpose of this prospective study is to determine the effectiveness and safety of the ThermiRF device in achieving overall submental lift.

In this study, “Lift” is defined as a ≥ 20 mm² lift of the submental area after the ThermiRF treatment.

A total of 70 male and female healthy volunteers between the age of 35 and 65 will be considered for this study. Subjects who sign the informed consent form and meet all entry criteria will be enrolled in this study and will be assigned a unique number/code to preserve confidentiality.

A total of six study visits are planned as described below:

- Visit 1: Screening visit – (Day 1)
- Visit 2: Single Treatment visit
- Visit 3: Day 30 safety assessment (± 7 to 14 days)
- Visit 4: Day 60 safety and Image capture for validation exercise (± 7 to 14 days)
- Visit 5: Day 90 safety and effectiveness follow-up visit (± 7 to 14 days)
- Visit 6: Day 180 safety and effectiveness follow-up visit - (± 7 to 14 days)

Photo images (2D and 3D) will be collected at Visits 1, Visit 4 (on first 30 subjects only), and at Visits 5 and 6 using a standard camera (2D) and the Vectra XT system (3D). The purpose of the photos are to quantitatively and qualitative evaluate treatment effectiveness using objective and subjective assessments to measure physical changes to the skin’s microstructure and aesthetic skin features over time.

A skin elasticity assessment using the Cutomer® will be collected at Visits 1 (screening), 5 (Day 90) and 6 (Day 180) to assess if any biomechanical changes of the skin occurred as a result of the ThermiRF treatment.

Safety assessments will be collected using the Numerical Rating Scale (NRS) a 10-point scale, and adverse events reports (observed or reported).

The overall study duration is approximately 12 months (i.e., 5-6 month recruitment period and 6 month study visits).

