11.2. Sample Size Determination

The sample size calculation is based on the following assumptions:

- The true response rate for subjects that do not drop out will be 70%.
- The null response rate is 45%, so a successful trial will reject the null hypothesis that the true response rate is less than or equal to 45%.
- The dropout rate will be approximately 12.5%. While some subjects that drop out may have data from Day 60 that can be carried forward in the primary effectiveness analysis, the sample size calculation assumes that none does and will therefore be treated as non-responders.
- The primary effectiveness analysis is based on a one-sided binomial proportion test that compares the null proportion to the alternative proportion.

Based on these assumptions, a minimum of 68 subjects is required to achieve 80% power at one-sided $\alpha = 0.05$, so a sample size of 70 subjects provides greater than 80% power.

Additionally based on the rule of three, sample size of at least 60 makes it possible to observe any adverse event that occurs with a frequency $> 5\%$ with 95% confidence.

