## 5 SAMPLE SIZE

The null and alternative hypotheses are:

$$\begin{aligned}
 H_0: \pi &\leq 0.45 \text{ (or 45\%)} \text{ vs.} \\
 H_a: \pi &> 0.45
 \end{aligned}$$

where  $\pi$  is the true proportion of subjects with at least 20 mm^2 lift. Under the assumptions that

1.  $\pi = 0.70$  (or 70%) for subjects not prematurely withdrawing from the study; and
2. The dropout rate is 12.5% and all dropouts will be considered as non-responders

a sample of size 70 enrolled subjects provides approximately 85% power to reject the null hypothesis in favor of the alternative at a one-sided  $\alpha=0.05$ .

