## 7.6 ASSESSMENT OF HOMOGENEITY

As this is a single-site study, no analysis will be performed for site homogeneity. Assessment of homogeneity across sex, age groups, and condition types will be performed as outlined in Section 12.

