### 12.2 AGE

To understand any potential differences amongst age groups which may be relevant to this study, the primary and secondary efficacy endpoints will be evaluated for age groupings (to be determined at time of analysis that creates an even dichotomous split) separately with the results side by side and presented in a table for the ITT analysis set. The purpose of this analysis is to assess consistency across the subgroups of age.

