**Figure 2. Bar chart for R0 and R9 output**

**Figure 3. Bar chart for R2, R5, and R7 output**

**Sponsor:** ThermiGen, LLC.  
**Protocol Number:** Thermi\_0005  
**Protocol:** *An Open-Label, Single-Center, Single-Treatment, Safety and Effectiveness Evaluation of Percutaneous Radiofrequency in Achieving Submental Lift*  
**Version:** Protocol Rev. A; SAP Rev. B

Table 8.1.1 Study Endpoints by Sex - Primary Endpoint ITT Population			
	Population	Male % (n/N) 95% CI [1]	Female % (n/N) 95% CI [1]
Improvement <math>\geq 20 \text{ mm}^2</math> at Day 90	ITT (missing subjects as failures)	XX.X (X/XX) (X.X, X.X)	XX.X (X/XX) (X.X, X.X))
	Subjects with missing data	XX	XX
	Subjects with Day 60 data carried forward	XX	XX
Improvement <math>\geq 20 \text{ mm}^2</math> at Day 90	ITT (excluding missing subjects)	XX.X (X/XX) (X.X, X.X)	XX.X (X/XX) (X.X, X.X)
	Subjects with Day 60 data carried forward	XX	XX

[1] Two-sided 95% Clopper-Pearson confidence interval.

Listing 8.1.1 Study Endpoints by Sex - Primary Endpoint					
Subject ID	Sex	Analysis Population	Day 60 Improvement [1]	Day 90 Improvement	Endpoint
XX-XXX	XX	XX	XX or N/A	XX or Missing	XX

**Sponsor:** ThermiGen, LLC.  
**Protocol Number:** Thermi\_0005  
**Protocol:** *An Open-Label, Single-Center, Single-Treatment, Safety and Effectiveness Evaluation of Percutaneous Radiofrequency in Achieving Submental Lift*  
**Version:** Protocol Rev. A; SAP Rev. B

Table 8.2.1.1 Study Endpoints by Sex - P-GAIS ITT Population with Available Data						
	Day 60 [1]		Day 90		Day 180	
	Male	Female	Male	Female	Male	Female
Assessment	% (n/N) 95% CI [2]					
Physician - Global Aesthetic Improvement Scale (P-GAIS)						
5 (Very Much Improved)	XX.X (X/XX) (X.X, X.X)					
4 (Much Improved)	XX.X (X/XX) (X.X, X.X)					
3 (Improved)	XX.X (X/XX) (X.X, X.X)					
2 (No Change)	XX.X (X/XX) (X.X, X.X)					
1 (Worse)	XX.X (X/XX) (X.X, X.X)					

[1] 30 subjects in sequential order of enrollment chosen for 60 day visit.

[2] Two-sided 95% Clopper-Pearson confidence interval.

Listing 8.2.1.1 Secondary Endpoint by Sex – P-GAIS						
Subject ID	Sex	Analysis Population	Day 60 [1]	Day 90	Day 180	
XX-XXX	XX	XX	XX	XX	XX	

**Sponsor:** ThermiGen, LLC.  
**Protocol Number:** Thermi\_0005  

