Mean ± SD (N)	N/A	N/A	XX.X ± XX.X (XX)			
Median (Min, Max)			XX.X (XX.X, XX.X)	XX.X (XX.X, XX.X)	XX.X (XX.X, XX.X)	XX.X (XX.X, XX.X)
95% CI [1]	N/A	N/A	(XX.X, XX.X)	(XX.X, XX.X)	(XX.X, XX.X)	(XX.X, XX.X)

[1] Two-sided 95% confidence interval of the percentage or the mean.

Listing 8.3.1 Study Endpoints by Sex - Exploratory Endpoint Elasticity					
Subject ID	Sex	Analysis Population	Baseline	Day 90 (Change from Baseline)	Day 180 (Change from Baseline)
XX-XXX	XX	XX	XX	XX (XX)	XX (XX)

NOTE: Tables 8.1.1, 8.2.1.1, 8.2.1.2, 8.2.1.3, 8.2.1.4 and 8.3.1 will be repeated for the Age (dichotomous or categorical group comparison) as 8.1.2, 8.2.2.1, 8.2.2.2, 8.2.2.3, 8.2.2.4, and 8.3.2 to support the planned subgroup analyses

**Sponsor:** ThermiGen, LLC.  
**Protocol Number:** Thermi\_0005  
**Protocol:** *An Open-Label, Single-Center, Single-Treatment, Safety and Effectiveness Evaluation of Percutaneous Radiofrequency in Achieving Submental Lift*  
**Version:** Protocol Rev. A; SAP Rev. B

Table 9.1				
Study Endpoints - Primary Endpoint				
PP Population				
	Population	% (n/N)	One-sided p-value[1]	95% CI[2]
Improvement <math>\geq 20</math> mm^2 at Day 90	PP	XX.X (X/XX)	X.XXX	(X.X, X.X)

[1] Null hypothesis is that the true percentage of subjects with  $\geq 20$  mm^2 improvement is less than or equal to 45%.

P-value is calculated based on the one-sided exact binomial test.

[2] Two-sided 95% Clopper-Pearson confidence interval.

Listing 9.1			
Study Endpoints - Primary Endpoint			
Subject ID	Analysis Population	Day 90 Improvement	Endpoint
XX-XXX	XX	XX	XX

**Sponsor:** ThermiGen, LLC.  
**Protocol Number:** Thermi\_0005  
**Protocol:** *An Open-Label, Single-Center, Single-Treatment, Safety and Effectiveness Evaluation of Percutaneous Radiofrequency in Achieving Submental Lift*  
**Version:** Protocol Rev. A; SAP Rev. B

Table 9.1.1 Study Endpoints – Qualitative Assessment for the 2D Imaging PP Population [1]		
	Percent Agreement	Kappa Statistic [2]
Overall		
	XX.X (X/XX)	X.XXX
Subgroups [3]		
Reader 1-2	XX.X (X/XX)	X.XXX
Reader 1-3	XX.X (X/XX)	X.XXX
Reader 1-4	XX.X (X/XX)	X.XXX
Reader 1-5	XX.X (X/XX)	X.XXX
Reader 2-3	XX.X (X/XX)	X.XXX
Reader 2-4	XX.X (X/XX)	X.XXX
Reader 2-5	XX.X (X/XX)	X.XXX
Reader 3-4	XX.X (X/XX)	X.XXX
Reader 3-5	XX.X (X/XX)	X.XXX
Reader 4-5	XX.X (X/XX)	X.XXX

[1] 30 subjects in sequential order of enrollment chosen for 60 day visit.

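### The sex and age subgroup tables are meant to assess consistency, but they contain no between-group difference and no criterion, so they do not directly measure it

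*SAP*

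**What the plan says.** SAP 7.6 sets the task: "Assessment of homogeneity across sex, age groups, and condition types will be performed as outlined in Section 12". SAP 12.1 then has the primary and secondary efficacy endpoints evaluated for each sex separately and shown next to each other. It gives the aim: "The purpose of this analysis is to assess consistency across the subgroups of sex". SAP 12.2 repeats this for age, with groups "to be determined at time of analysis that creates an even dichotomous split".

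The SAP shells show what will be produced. Table 8.1.1 has one column per sex, each with a percentage and an interval that the footnote defines as "Two-sided 95% Clopper-Pearson confidence interval". The secondary-endpoint shells (8.2.1.1 to 8.2.1.5) follow the same pattern. The elasticity shell (8.3.1) gives a mean and interval per sex. No Table 8 shell has a difference, ratio, interaction term or p-value. A note after Listing 8.3.1 says that a list of these tables "will be repeated for the Age (dichotomous or categorical group comparison"). The list leaves out Table 8.2.1.5, the blinded 2D panel.

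Neither Section 12 nor the shells state what result would count as consistent or inconsistent.

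**The concern.** Consistency across two groups is a statement about the difference between them. Two separate intervals describe each group on its own. They leave readers to make the comparison by eye, and different readers can fairly reach different answers from the same table. One common habit, checking whether the two 95% intervals overlap, is much stricter than a 5% comparison and lets sizeable differences pass. Another, checking each interval against the 45% null rate, can suggest inconsistency where none exists. At stake is what the report can say about whether the device works similarly in men and women and in younger and older subjects. The primary conclusion is not at stake.

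Three mismatches sit beside this. SAP 7.6 names condition types, which Section 12 never takes up. SAP 12.2 fixes an even two-way age split, while the shell note also allows a categorical one. SAP 12.2 covers the secondary endpoints, but the list of age repeats drops the blinded panel, which SAP 4.1.2 lists as a secondary endpoint.

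**Working it through.** **Inputs from the documents.** N = 70, null rate 45%, one-sided alpha 0.05, response rate 70% in subjects who stay in, and dropout 12.5% counted as non-response (SAP 5; Protocol 11.2). The expected ITT response rate is therefore 0.70 × 0.875 = 0.6125.

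**The plan's own figure.** SAP 5 says "a sample of size 70 enrolled subjects provides approximately 85% power". The exact one-sided binomial test at N = 70 rejects with 39 or more responders (actual alpha 0.0467). Its power at 0.6125 is 85.8%, so the stated figure reproduces. The documents give no power or precision for subgroups.

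**Inputs assumed.**
- Split: 35/35. For age this follows from the even split of 70. For sex it is only an assumption, because the protocol says "A total of 70 male and female healthy volunteers" and gives no ratio.
- True subgroup rates: 0.6125 plus and minus half the true difference. For scale, the gap between the design rates is 70% − 45% = 25 points.

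**Formulas.**
- Clopper-Pearson limits for x of n: the 0.025 quantile of Beta(x, n − x + 1) and the 0.975 quantile of Beta(x + 1, n − x).
- Newcombe limits for d = p1 − p2, with Wilson limits (l1, u1) and (l2, u2): d − √[(p1 − l1)² + (u2 − p2)²] and d + √[(u1 − p1)² + (p2 − l2)²].
- Each probability sums Bin(x; 35, pA) × Bin(y; 35, pB) over all pairs (x, y) that meet the condition.

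**Results at 35/35.**

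| True difference | Rates | Separate 95% intervals overlap | 95% CI for the difference excludes 0 | Observed percentages at least 20 points apart |
|---|---|---|---|---|
| 0 | 61.25 / 61.25 | 99.8% | 5% | 11% |
| 10 | 66.25 / 56.25 | 98.5% | 14% | 24% |
| 20 | 71.25 / 51.25 | 91% | 40% | 55% |
| 25 | 73.75 / 48.75 | 81% | 58% | 72% |
| 30 | 76.25 / 46.25 | 67% | 74% | 85% |
| 40 | 81.25 / 41.25 | 31% | 95% | 98% |

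The overlap probability falls below one half between 34 points (53%) and 35 points (49%).

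**Uneven splits.** At a true 25 points the intervals overlap in 84–85% of trials at 21/49, 89–90% at 14/56 and 95–99.6% at 7/63, depending on which group has the higher rate.

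**One possible result.** Suppose 26/35 against 17/35. The separate intervals are 56.7–87.5% and 31.4–66.0%, which overlap. The difference is 9/35 = 25.7 points, with Newcombe 95% CI 2.9 to 45.1.

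**A different reading of the same table.** If each interval is judged by whether it lies above 45%, the two subgroups disagree in 46% of trials with no true difference, and in 87% at a true 25 points.

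**Precision of the added interval.** At a common rate of 0.6125 the large-sample half-width is 1.96 × √[0.6125 × 0.3875 × (1/35 + 1/35)] = 0.228, about 23 points. Newcombe averages about 22. The same large-sample formula gives about 25 points at 21/49, 29 at 14/56 and 38 at 7/63.

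**The case against.** Descriptive side-by-side tables are a defensible choice in a single-arm study of 70, and SAP 7.5 already disclaims formal testing of secondary endpoints for labelling. The percentages are printed next to each other, so a reader sees the gap: at a true 30 points they differ by 20 or more in 85% of trials. Each cell carries n/N, so anyone can work out the difference and its interval for a binary endpoint. SAP 12.3 leaves room for further subgroup analyses. The fix also buys limited power: the difference interval still misses a true 20-point gap about 60% of the time, and 80% power for 25 points needs about 59 per subgroup.

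Most of this stands, and it limits the point. A reader might infer that a real sex or age difference would usually be reported as consistency. The documents do not support that. They never make overlap the rule, the visible percentages pull the other way, and even under an overlap rule at 35/35 a 40-point difference is flagged 69% of the time. Under the 45% reading the error can run the other way. Nor is it right that the output cannot be used at all, since the counts allow the comparison.

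What the objection does not remove is the gap between aim and output. The SAP sets a between-group question, plans no between-group quantity, and leaves the reading open. A permission to add analyses later is not a plan to report the difference. Small numbers are a reason to show the uncertainty of the difference.

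**Conclusion.** The point holds as a modest improvement. SAP 7.6, 12.1 and 12.2 set out to assess homogeneity or consistency, and the Table 8 shells supply only within-group estimates, with no difference and no criterion. That needs no assumption beyond reading the documents. The size is conditional. If a reader judged by interval overlap at a 35/35 split around 61.25%, differences of 20 to 30 points would pass in 91% down to 67% of trials, against 40% up to 74% in which a 95% CI for the difference would exclude zero. The subgroup effects are assumed, and so is the sex split. The small subgroups share the blame, because no analysis of 70 subjects can show consistency closely. The three mismatches are drafting matters and do not depend on these figures.

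**What to change.** In SAP 12.1 and 12.2, and in Table 8.1.1 and its age repeat 8.1.2, add the difference in Day 90 response rate between the two groups with a two-sided 95% CI (for example Newcombe), labelled descriptive. Do the same for the binary secondary endpoints. The GAIS and blinded-panel subgroup shells list only the five categories, so they also need a row for the dichotomised response defined in SAP 10.2.

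Add Table 8.2.1.5 to the age repeats so that the shells match SAP 12.2. Reconcile the shell note's categorical option with the even split in 12.2, and the condition types in 7.6 with Section 12. The author should settle whether a subgroup was left out or the words are left over.

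The cost is SAP wording and a row or two per subgroup table, with no new data and no change to the primary test or its alpha. The downside is a wide interval, about plus or minus 22 to 23 points at 35/35 and wider if the sexes are uneven. The text should say that an interval including zero does not show consistency.
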